6. *Self-Regulation Mechanisms Hypotheses:* In 4 different fMRI tasks, we hypothesize (a) greater activation of anterior cingulate cortex (ACC) and medial orbitofrontal cortex (OFC) and decreased activation in amygdala/hippocampus after MTPC intervention compared to before intervention (i.e. a pre-post increase) in an emotional Go/NoGo inhibitory control task; (b) greater activation of insula after (compared to before) MTPC in a self-compassion task (that contrasts self-reassurance conditions with a self-criticism condition); (c) greater insula activation during an interoceptive attention task (that contrasts an interoceptive attention condition with an exteroceptive attention condition); and (d) greater rostral ACC (rACC) and ventromedial prefrontal cortex (vmPFC) activation during the anticipation of pain and greater activation in the lateral prefrontal cortex (LPFC) and somatosensory areas during pain in an emotion/pain regulation task, after compared to before the MTPC intervention.
We hypothesize that all inhibitory control and interoceptive targets will be associated with higher levels of initiation of regimen adherence, while self-compassion, interoceptive targets and emotion/pain regulation will be associated with higher levels of regimen maintenance.

HEART Pilot Study Hypotheses

7. ***HEART pilot study validation goal:*** Our goal is to implement activity and heart-rate tracking, nutrition, sleep, and mindfulness practice tracking in a cohort of MINDFUL-PC alumni to determine whether this suite of behavioral monitoring tasks can behaviorally validate the signal from the self-reported action plan initiation protocol.

We hypothesize that self-reported action plan initiation with activity, diet, sleep or mindfulness practice will be associated with a behavioral change as assessed with the daily tracking devices.

8. ***HEART pilot study concurrent cohort:*** We hypothesize that participants who are in an 8-week MTPC group will demonstrate higher levels of action plan initiation, with an associated change in behavioral monitoring, than participants who are randomized to the waitlist condition. We also hypothesize that participants who chose to increase activity will have a greater increase in daily activity than those who chose a diet-, mindfulness- or sleep-related action plan goal.

B. Background and Rationale:

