The **Perceived Control Questionnaire (PCQ)** is adapted from a 5-item perceived control measure from Jerant et al. [55] and a previously validated survey from Armitage et al. [56]. This 5-item scale ask participants to rate their sense of control over chronic illness self-management on a 7-point scale from 1 (*None*) to 7 (*Total*). Items include "How much personal control do you have over your self-management behaviors?" Duration: 3 min.

Action Plan Worksheet/SMART Goal Video: Patient participants will complete the Action Plan Worksheet and watch a brief video about creating SMART goals (for example, <https://www.youtube.com/watch?v=1-SvuFIQjK8>) in PT Study Week 7. The Action Plan Worksheet is a 13-item worksheet that incorporates information about SMART goals to support patient participants to make a goal about their health in one of 3 categories (activity level/exercise, diet/eating/drinking, or mindfulness meditation practice). Patients are encouraged to share this worksheet with a person who may help the patient in accomplishing the goal, and/or a healthcare provider. Duration: 15 min.

Patients will complete the self-report **Action Plan Assessment (APA-10)** questionnaire after filling out the Action Plan Worksheet, at PT Study Week 7. This survey instrument is developed as an adaptation of two self-determination theory scales [57] [58] and incorporates elements of shared decision-making [59] and self-efficacy and barrier appraisal [60]. This 10-item scale evaluates patient behavior in the domains of self-determination, motivation, shared decision-making, and barrier appraisal. Participants are asked to rate their agreement with a statement on

a 7-point scale from 1 (*Strongly Disagree*) to 7 (*Strongly Agree*). A sample item includes “I have agreed to this action plan because I want to do it for myself.” Duration: 5 minutes.

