Food, Activity, and Sleep Tracking (FAST) Questionnaire: Participants will be asked to fill out a daily questionnaire about their food, activity, and sleep tracking. The survey is adapted from the Automated Self-Administered 24-Hour Dietary Assessment Tool (ASA24) and the National Sleep Foundation Sleep Diary.

The ASA24 was released in 2009 by the NIH and the National Cancer Institute as a web-based tool that enables multiple, automatically coded, self-administered 24-hour recalls. This tool was designed for use by research participants, clinicians, patients, and students. The ASA24 asks detailed questions about food form, preparation, portion size, and additions using an extensive branching logic database. The ASA24 was designed to be culturally sensitive and accessible by individuals using assistive technologies. Features of the ASA24 respondent website can be found here (<https://epi.grants.cancer.gov/asa24/respondent/features.html>). A demo version of the respondent site can be found here (<https://asa24.nci.nih.gov/demo/>).

The FAST Questionnaire asks participants what time they went to bed, what time they got out of bed, the total hours slept, any naps taken during the day, then about the timing and amount of alcoholic and caffeinated drink consumption. It also asks if they exercised throughout the day and then further asks how long they performed each type of exercise.

The food tracking portion asks subjects what main meals they ate in a day. For each main meal, subjects are asked how fast they ate, what they were doing while they ate, what food groups were included in their meals, and how much they ate. It also asks subjects if they ate any food outside of their main meals, and then asks how many times they eat each type of food.

Duration: 10 minutes.

Action Plan Creation – Participants in the **concurrent cohort** of the HEART pilot study will fill out the Action Plan Worksheet, the APA-10, and the APIS-5 as regularly scheduled for the main MINDFUL-PC study. Participants in the **alumni cohort** of the HEART study will fill out the Action Plan Worksheet and the APA-10 at the end of HEART study Week 3. They will fill out the APIS-5 at the end of HEART study Weeks 4 and 5.

Action Plan Creation Duration: 20 minutes

[figure not shown]
Action Plan Initiation Survey Duration: 5 minutes

Behavioral Tasks

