Self-Regulation hypothesis testing for the fMRI data will be performed as follows. For each of the 4 fMRI tasks, we will use a Linear Mixed Effects model of the BOLD signal in the ROIs associated with that task (described above), with 2 time points (pre- and post-intervention). The

model will include the following regressors of interest: gender, age, and the following pre-intervention scores: depression (PROMIS-DSF), anxiety (PROMIS-ASF), self-compassion (SCS-SF), and mindfulness (FFMQ); and the following regressors of no interest: head motion parameters and cardiac and respiratory components of physiological noise. Hypothesis will be expressed as: Is there any significant difference between the 2 time points in the task-specific ROI activation during a) NoGo trials versus Go trials, b) self-reassurance versus self-criticism, c) Interoception-versus-Exteroception, and d) expectation of pain and pain versus rest. The null hypothesis will be that the ROI activation at the 2 time points are not significantly different. Significance testing will be done using permutation/bootstrapping methods (see [79, 80]).

1. HEART pilot study analysis plan: The HEART pilot study aims to recruit 40 participants in the **alumni cohort** and 30 participants (10-20 in the waitlist arm and 20-40 in the intervention arm) in the **concurrent cohort** for a total of 70 participants. The data would be examined for correlations between the action plan initiation 7-item survey and pre-post differences in step count, the number of active periods, changes in sleep duration, changes in mindfulness practice, and change in nutritional habits depending on which action plan goal was specified in the patient action plan. We will also examine the percentage of action plan initiation events ≥ 5 on the APIS-5 that have a corresponding behavioral change evidenced in the daily data collection. Finally, we will also examine whether the activity changes are greater in the participants who selected exercise as compared to those who selected nutrition or dietary changes and vice versa.

C.5.c. Sample Size calculations:

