The HEART pilot study is underpowered to be able to compare between-group differences in outcomes, but the primary aims of the pilot study are 1) to demonstrate feasibility of using

commercially available activity/sleep/diet trackers and online daily surveys for ecological behavior tracking in a MBI RCT and 2) to use the daily behavior tracking to validate the action plan goal setting process and the self-report action plan initiation measure. To do this we aim to recruit the 70 participants from both the alumni and concurrent phases and then to examine the data for correlations between the action plan initiation 7-item survey and pre-post differences in step count, the number of active periods, changes in sleep duration, changes in mindfulness practice, and change in nutritional habits depending on which action plan goal was specified in the patient action plan. When conducting correlation analysis with 70 participants, using $\alpha = 0.05$ type 1 error rate, we would have 80% to find a correlation coefficient of 0.33. If we have lower than expected recruitment and only had 47 participants for correlation analysis, using $\alpha = 0.05$ type 1 error rate, we would have 80% to find a correlation coefficient of 0.4, which represents moderate correlation⁹⁶. We will also examine whether the activity changes are greater in the participants who select exercise as compared to those who selected nutrition or dietary changes and vice versa.

D.4.d. Stopping Rules:

This study will be stopped prior to its completion if: (1) the intervention is associated with adverse effects that call into question the safety of the intervention; (2) difficulty in study recruitment or retention will significantly impact the ability to evaluate the study endpoints; (3) any new information becomes available during the trial that necessitates stopping the trial; or (4) other situations occur that might warrant stopping the trial.

D.4.e. Designation of an Independent Monitor:

The Independent Monitor for this study is [name], MD at Boston Medical Center. [name] is not associated with this research project and thus works independently of the PI, [name]. [name] is not a part of the key personnel involved in this grant, and is qualified to review the patient safety data generated by this study because of her unique expertise in the area of mindfulness training for primary care patients.

D.4.f. Safety Review Plan:

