The HEART Pilot study is intended to test the feasibility of using commercial behavior tracking smartphone applications and devices in the context of the action planning and initiation process of the MINDFUL-PC study, as well as to validate with objective behavioral measures, the self-report action plan initiation survey. We are not pilot testing the devices and applications themselves but are pilot testing their use in our studies. Due to the rapid innovations in the consumer market, we have left open the possibility of using other, improved but similar applications for activity, sleep, and diet tracking. The Argus App is among the current best possible apps for this purpose. Below is a list of similar alternatives.

We are considering the following smartphone activity tracking applications for inclusion in the study as alternatives to the Argus App:

- Pedometer for Android
- Stepz for IOS.
- Activ8 by 2M Engineering

We are considering use of the following activity tracking devices for inclusion in the study:

- Fitbit
- Moov
- Jawbone
- Withings
- MD2K Cerebrum
- Garmin Vivosmart

1. Bornemann, B. and T. Singer, *Taking time to feel our body: Steady increases in heartbeat perception accuracy and decreases in alexithymia over 9 months of contemplative mental training*. *Psychophysiology*, 2017. **54**(3): p. 469-482.
2. Hendrickson, K.L. and E.B. Rasmussen, *Effects of mindful eating training on delay and probability discounting for food and money in obese and healthy-weight individuals*. *Behav Res Ther*, 2013. **51**(7): p. 399-409.
3. Ashe, M.L., M.G. Newman, and S.J. Wilson, *Delay discounting and the use of mindful attention versus distraction in the treatment of drug addiction: a conceptual review*. *J Exp Anal Behav*, 2015. **103**(1): p. 234-48.
4. Morrison, A.B., et al., *Taming a wandering attention: short-form mindfulness training in student cohorts*. *Front Hum Neurosci*, 2014. **7**: p. 897.
5. Guck, T.P., et al., *Attributions regarding unmet treatment goals after interdisciplinary chronic pain rehabilitation*. *Clin J Pain*, 2008. **24**(5): p. 415-20.
6. Margolin, A., et al., *A controlled study of a spirituality-focused intervention for increasing motivation for HIV prevention among drug users*. *AIDS Educ Prev*, 2006. **18**(4): p. 311-22.
7. Arozullah, A.M., et al., *Development and validation of a short-form, rapid estimate of adult literacy in medicine*. *Med Care*, 2007. **45**(11): p. 1026-33.

REFERENCES

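### HEART's objective, device-based validation of self-reported action plan initiation covers activity goals only; for diet, sleep and mindfulness practice it compares one self-report with another

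*Combined protocol and SAP*

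**What the plan says.** Appendix A (Choice of Smartphone Applications and Tracking Devices) gives one purpose of HEART as "as well as to validate with objective behavioral measures, the self-report action plan initiation survey". Hypothesis 7 in A.2.b says that self-reported "initiation with activity, diet, sleep or mindfulness practice will be associated with a behavioral change as assessed with the daily tracking devices". D.4.c makes validation of the self-report initiation measure the second primary aim of the pilot.

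The analysis plan in C.5.b correlates the initiation survey with "pre-post differences in step count, the number of active periods, changes in sleep duration, changes in mindfulness practice, and change in nutritional habits", the criterion depending on the participant's goal. It also reports the percentage of initiation events that have a matching behavioural change in the daily data. C.5.b item 5 lists the same behaviours as validating initiation. D.4.c repeats the correlations and gives 80% power for a correlation of 0.33 with 70 participants and 0.4 with 47.

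The measures are in C.3.d.4, C.3.f.7 and the HEART schedule in Appendix A. A phone application counts steps, and a wristband activity tracker may be added if judged feasible. For FAST, "Participants will be asked to fill out a daily questionnaire about their food, activity, and sleep tracking"; it covers bed times, hours slept, meals and exercise. Mindfulness practice is recorded in a diary.

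On goals, the Action Plan Worksheet in C.3.f.6 offers "one of 3 categories (activity level/exercise, diet/eating/drinking, or mindfulness meditation practice". The APIS-5 description in the same section lists six categories, sleep among them, and Hypothesis 8 in A.2.b refers to a sleep-related goal.

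**The concern.** A validation study needs a criterion whose errors are not shared with the measure being validated. The same participant completes the APIS-5, FAST and the diary. Someone who reports that a plan was started has a reason to report the behaviour as changed too. Agreement can then arise from reporting alone, yet the wording in A.2.b and Appendix A would let it be read as confirmation by device.

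The percentage of initiation events with a behavioural change is the most exposed result. As written, a diary entry and a rise in step count would each count as one confirmed event. FAST also asks about exercise, so even for activity the criterion should be fixed in advance as device data.

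This matters beyond HEART because action plan initiation is the endpoint in the main trial's sample size calculation (C.5.c, D.4.c). A claim that it has been objectively validated would support how the main result is read.

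**Working it through.** **Step 1: match each domain to its source.**

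| Domain | Criterion (C.5.b, D.4.c) | Source (C.3.d.4, C.3.f.7) | Worksheet goal | APIS-5 category |
|---|---|---|---|---|
| Activity | step count; active periods | phone app, wristband if feasible | yes | yes |
| Diet | nutritional habits | FAST, self-completed | yes | yes |
| Mindfulness practice | amount of practice | diary, self-completed | yes | not by name |
| Sleep | sleep duration | FAST, self-completed | no | yes |

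Active periods are taken here as device output, although the battery names only steps for the app. Device-based criteria are then 2 of 5 and self-report criteria 3 of 5. One of the three worksheet goals has a device criterion. The heartbeat, discounting and sustained-attention tasks measure none of the goal behaviours.

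**Step 2: reproduce the stated power.** With Fisher's z at two-sided 0.05 and 80% power, n = ((1.960 + 0.842) / atanh(r))² + 3.

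- r = 0.33: atanh = 0.3428; (2.802 / 0.3428)² + 3 = 69.8, so 70.
- r = 0.40: atanh = 0.4236; (2.802 / 0.4236)² + 3 = 46.7, so 47.

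Both match D.4.c. One-sided testing would give 56 and 38, so the plan's figures are two-sided.

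**Step 3: apply this to participants with a device criterion.** The documents do not say how many will choose an activity goal, so the share is an assumption, shown as a range. Detectable r = tanh(2.802 / √(n − 3)); power for 0.33 = Φ(0.3428 × √(n − 3) − 1.960).

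| Share of 70 choosing activity | n | Detectable r at 80% power | Power for r = 0.33 |
|---|---|---|---|
| 25% | 18 | 0.62 | 26% |
| one third | 23 | 0.56 | 34% |
| 50% | 35 | 0.46 | 49% |
| 60% | 42 | 0.42 | 57% |

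For one third: √20 = 4.472; 2.802 / 4.472 = 0.627, whose tanh is 0.556; and 0.3428 × 4.472 − 1.960 = −0.427, for which Φ is 0.335. With the minimum of 47 participants, one third (n = 16) gives a detectable r of 0.65, and one half (n = 24) gives 0.55.

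**Step 4: sleep.** C.5.b includes "changes in sleep duration, changes in mindfulness practice, and change in nutritional habits depending on which action plan goal was specified". If the worksheet governs, no participant can have set a sleep goal and this criterion has no goal group. If the APIS-5 list governs, there may be one. The text does not settle which.

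**The case against.** Several points on the other side stand.

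- **Self-report is disclosed.** The aim in A.2.a and D.4.c names "commercially available activity/sleep/diet trackers and online daily surveys for ecological behavior tracking", and FAST is openly called a questionnaire. The overstatement lies in Hypothesis 7 and Appendix A; C.5.b and D.4.c do not call the measures objective.
- **Change scores help.** The criteria are changes from a baseline week, so a participant's stable over-reporting cancels. A shift in reporting after a goal has been set does not.
- **The correlations are goal-specific.** C.5.b also compares activity change between participants with exercise goals and those with dietary goals, a specificity check that device data can support. The pooling problem therefore concerns mainly the percentage of confirmed events.
- **HEART is a feasibility pilot.** It says it is underpowered for between-group comparisons, and nothing here alters the main trial's treatment comparison.

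Appendix A leaves room for other sleep and diet apps, but none is a current measure. C.1.c.3 and D.1.a still mention food pictures, but no listed HEART task collects them. Neither supplies a device criterion.

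Three stronger readings are tempting and not supported. A reader might infer that sleep is not a goal at all; the APIS-5 categories and Hypothesis 8 say otherwise, so this is a conflict to reconcile. A reader might infer that most participants would be validated only against self-report; that holds by count of goals and criteria, but no goal distribution is given. A reader might put a figure on the inflation by assuming some shared reporting variance; the documents give no such value, and a simple shared-variance model ignores what differencing removes.

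**Conclusion.** The point holds as a mismatch between claim and measures. Device-based validation is available for activity only. For diet, sleep and mindfulness practice the planned evidence is agreement between two self-reports by one person, with a possible bias of unknown size.

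The stated power is arithmetically right for 70 pairs. If each participant contributes only the criterion that matches the chosen goal, 70 is reached only by combining device and self-report criteria. For activity goals alone the detectable correlation is about 0.56 if one third choose activity, and 0.62 to 0.42 across assumed shares of 25% to 60%, against the stated 0.33. These figures rest on the assumed share, on two-sided testing and on full recruitment to 70.

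This limits what HEART may conclude. It does not invalidate the pilot or the main trial.

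**What to change.** 1. In A.2.b (Hypothesis 7) and Appendix A, limit objective or device-based validation to activity goals.
2. In C.5.b (item 5 and the HEART analysis plan) and D.4.c, name device step count and active periods, not the FAST exercise items, as the activity criterion, and say which device supplies active periods.
3. In the same places, report diet, sleep and mindfulness practice separately as agreement between self-reports. Do not pool them with device-confirmed events in the percentage of initiation events with a behavioural change.
4. In D.4.c, state that 80% power for 0.33 with 70 participants does not describe the activity-goal subset, and give the detectable correlation over a range of plausible shares.
5. Reconcile the goal categories in A.2.b and C.3.f.6. If the worksheet governs, analyse sleep duration only as an off-target behaviour.

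This changes protocol and analysis text only; no new data are needed. The cost is a narrower objective-validation claim that rests on fewer participants, with the lower power shown above.
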